- **Measures.** We are including (1) demographic (age, sex, race/ethnicity, living situation, etc.), (2) anthropometric and cardiometabolic (lipids, insulin, glucose, blood pressure, HbA1c) (**Table 2**); (3) health-related quality of life (HRQOL)⁹³; and (4) process measures (feasibility, acceptability of intervention content/delivery, guided by the RE-AIM [Reach, Efficacy, Adoption, Implementation, Maintenance] framework⁹⁴⁻⁹⁶) in the proposed study. We will also include standard-of-care pre-post MBS physical activity (past 7-day step counts, 24-hour diet recall assessments and the Family Assessment Device-12 item (parent and adolescent report of affective responsiveness and involvement, and problem solving within one's family); Clinical Measures. Anthropometric and cardiometabolic data will be collected at baseline and at 3- and 6-months post MBS as part of standard of care. All blood samples are documented in the Electronic Health Record. HRQOL. At 1 month pre- and 6-months post-MBS, we will administer the CDC's HRQOL-14 Healthy Days Measure. This survey includes 3 modules (Healthy Days Core Module = 4 questions, Activity Limitations Module = 5 questions, and the Healthy Days Symptoms Module = 5 questions). This instrument has been validated in the study age group.⁹⁷ SDOH. Literacy, social, food, driving, financial, and housing needs, and tobacco use.
- **Process Measures.** Qualitative/quantitative process measures will be collected across all intervention sessions via embedded short surveys and at 6-months post-MBS to assess: acceptability (content was appropriate, interesting, easy to use), feasibility (recruitment, retention & adherence rates), and sustainability (perceived barriers/facilitator to intervention implementation, strategies) of the lifestyle intervention. All process measures will be guided by the RE-AIM framework which is particularly appropriate for assessing the fit and relevance of interventions in real-world settings.⁹⁴⁻⁹⁶

The PI has integrated RE-AIM in her past obesity work.^{31,98}

- **Data Analysis Plan.** The AIM 3 dependent measure for each dependent effect will be based on the change from pre to post-MBS weight loss cardiometabolic resolution measurements (**Table 2**). Proportions and means will be the primary scales of the dependent outcomes used to evaluate Table

Table 2. Anthropometric and Cardiometabolic Outcome Measures	
Anthropometrics	Instrument

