(1) Raw Weight Loss	Digital scale (to nearest 0.1 pounds) with the participants wearing light clothing, no shoes.
(2) Body Mass Index (BMI)	Digital scale and height (to nearest 0.5 cm, via Accustat Genentech stadiometer)
(3) Excess Weight Loss (EWL)	Pre-MBS weight - follow up weight)/(Pre-MBS weight - ideal body weight) × 100%

2 outcomes. We will use the Generalized Linear Model (GZLM) to model the impact of the intervention developed in AIM 2 for dependent effects.

Much like the General Linear

(4) Body Composition	InBody570 body composition analyzer- muscle, fat and total body water measures
Comorbidity Resolution	
(1) Cardiometabolic Profile	lipids, insulin, glucose, blood pressure

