Model that allows for variation in type and scale characteristics of the independent effects, the GZLM extends this versatility to include various types of dependent variables.⁹⁹ In GZLM, the relationship between the independent variables and the dependent outcomes is specified by way of a link function that defines the functional form of this relationship (e.g., when the dependent variable is a proportion, a logistic link function might be used). Through different specifications of the link and probability functions, one generalized model is used to examine the statistical relationships between the design parameters (i.e., independent variables) and the dependent variables, regardless of their scale properties. Statistical consideration is given to repeated measures (pre-, 3-, 6-month post-MBS data). Since the time component has only 2 levels (e.g., 1 pre, 2 post-MBS), there are minimal statistical complications associated with the autocorrelation structure of repeated measures. Measures taken at baseline will be included in the GZLM as covariates to ensure pretest balance and as a control on regression to the mean. Changes in weight will be analyzed by employing a generalization of the t-test, known as Hetelling's T² test. This approach is very important in this case, since it same approach employed in the design. We shall assume a more conservative type I error of 1% to adjust for multiplicity.¹⁰⁰ Missing Values: GZLM models will efficiently use the longitudinal data and accommodate attrition that is ignorable (essentially, missing at random, MAR).¹⁰¹ To assess sensitivity to MAR we will use approaches for the multivariate normal setting and others if normality is not reasonable.¹⁰¹ This avoids the problem of eliminating subjects with incomplete repeated measurements. SAS and JMP (SAS Institute, Cary, NC) will be the primary statistical software packages. *Quality Control.* PI [name] will coordinate the QA/QC protocol with clinical and research staff. Appropriate checks will be conducted prior to, during, and after the completion of data collection.

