- **Statistical Power for AIM 3.** A single-factor, repeated measures design with a sample of 20 subjects, measured at baseline, 3-, and 6-months, achieves 80% power to detect a contrast using a multivariate T² test at a 0.01 significance level. We reduce the type I to a more conservative 1% to correct for multiplicity. The standard deviation across subjects at the same time point is assumed to be 1. The pattern of the covariance matrix is to have all correlations equal with a correlation of 0.25 between the first and second time point measurements.¹⁰⁰⁻¹⁰³ The value of the contrast applied to the hypothesized means is 1.⁹⁷ However, since we are anticipating an attrition rate of ~10%, we will recruit 22 adolescent MBS patients.

Data and Safety Monitoring

- *Data and Safety Monitoring:* All subjects will have an assigned unique study identification number used on all data forms and instruments. Data are computer-linked to the remainder of the dataset on

each individual, and linking information between personal identifiers and study numbers is kept in a locked file cabinet in the Principal Investigator's Office. Certain program staff (e.g., principal investigator, clinical team of [name], [name], and [name], study coordinator) will have access to confidential information needed to perform their respective duties, but the rest of the research staff are not privy to confidential information.

- *Potential Adverse Events.* None of the proposed procedures involve invasive methods of data collection. Most of the proposed methods are part of, or an extension of, the standard of care to assess pre-post MBS surgery mental and physical health and are minimal risk. These studies present minimal discomforts to the patient. Should any adverse events occur during this protocol, the medical facilities at University of Texas are prepared to care for the study participants. All participants will be debriefed regarding any serious health information that might be discerned in the protocol.
- *Description of Adverse and Serious Adverse Events:* Adverse events and serious adverse events identified for study participants that will be reported during protocol are: Adverse Events
 1. Family Crises
 2. Possible Violation of Confidentiality
 3. Extreme Distress due to Assessment Procedures
 4. Extreme Embarrassment or Distress in
Response to Disclosing Sensitive Personal Information

Serious Adverse Events

1. Suicidal Thoughts or Attempts
2. Abuse

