- This study was designed around the maximum sample size possible given the logistical limitations of the study (time, expense). For a total sample size of 25 subjects (Aim 3, the power associated with any of the independent effects in any of the proposed statistical models will be approximately 80% (P value cutoff = .01) as long as the effect accounts for 3% of the total variance relative to the model specific error term (i.e., $R^2 = .03$). This will be true for any effect that is included in any of the statistical models either pre or postoperative and includes both main effects and possible interactions. The power will change slightly due to the complexity of the model and the number of independent effects included, but overall, considering the tradeoff between increased efficiency and loss of error degrees of freedom in more complex models, the power will remain at approximately 80% when 3% of the variance is explained. This axiom also holds no matter the scale of measurement (i.e., continuous or discrete). An R^2 of .03 equates to a "d" statistic (i.e. Cohen's d) of approximately .35. According to Cohen's taxonomy for the social sciences, this is a small to medium effect size. Effects accounting for less than 3% of the total variance are most likely of limited clinical significance. As previously stated in the statistical methods, considering the observational nature of the investigation, we have chosen to use a more conservative P value cutoff. More importantly this conservative standard also increases the chances of reproducibility and helps to account for the amount of statistical modeling/testing that increases the likelihood of irreproducible results.

Ethics

- For all study participants the initial consent process will take place during recruitment process by clinical staff and research staff. However, if a willing participant does not have time to learn about, and sign all consent forms, study staff will schedule a follow up time with them to consent. If needed participants will be allowed to take consent home to review before speaking to research staff or clinical staff administer consent.

Data handling and record keeping

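### The claim that power stays near 80% on any scale of measurement is wrong, and the plan does not say whether the co-morbidity outcomes are analysed as means or as proportions

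*Combined protocol and SAP*

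**What the plan says.** Under Study Measures, the Data Analysis Plan bases the AIM 3 dependent measure on "change from pre to post-MBS weight loss cardiometabolic resolution measurements". It continues: "Proportions and means will be the primary scales of the dependent outcomes used to evaluate Table" 2 outcomes. Both scales are therefore primary, and no sentence says which outcome goes on which scale.

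Table 2 has two groups. The anthropometric group holds weight loss, BMI, excess weight loss and body composition. The co-morbidity resolution group holds one entry, a cardiometabolic profile made up of "lipids, insulin, glucose, blood pressure". There is no cut-off and no definition of a resolved co-morbidity.

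The model is a generalized linear model, with the remark that "when the dependent variable is a proportion, a logistic link function might be used". The same section assigns the Hotelling T² test to changes in weight.

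Statistical Power for AIM 3 says that 20 subjects measured at three time points "achieves 80% power to detect a contrast using a multivariate T² test at a 0.01 significance level", with SD 1, equal correlations of 0.25 and a contrast value of 1. On the significance level it says: "We reduce the type I to a more conservative 1% to correct for multiplicity".

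The Statistics section claims approximately 80% power for any effect in any of the models, and adds: "This axiom also holds no matter the scale of measurement (i.e., continuous or discrete)".

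**The concern.** Lipids, insulin, glucose and blood pressure are continuous and are collected at baseline and at 3 and 6 months after surgery. Reducing each to normal or abnormal discards information, and at 20 subjects and a 1% level the loss is large. The plan tells the reader that this choice does not affect power, and it leaves the choice open.

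Two things are at stake. A reader who relies on the Statistics section would take a non-significant yes/no result as coming from a test with about 80% power, when the true figure could be a small fraction of that. And because both scales are primary and neither is assigned, the scale for these measures could be settled after the data are seen.

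**Working it through.** **Inputs from Statistical Power for AIM 3.** n = 20, α = 0.01, SD 1, all correlations 0.25, contrast value 1. Sidedness is not stated; two-sided is assumed because T² is non-directional. The contrast coefficients and mean vector are not given.

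**Step 1: reproduce the plan's figure on a continuous scale.**

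- *Baseline versus one post visit.* SD of the change = √(2 × (1 − 0.25)) = 1.225. Noncentrality = √20 × 1 / 1.225 = 3.65. Critical t (19 df) = 2.861. Power = 77.4%; with n = 21 it is 80.3%.
- *Two-df T² on the two change scores.* Their covariance matrix has 1.5 on the diagonal and 0.75 off it. For means (0, 1, 1) or (0, 0, 1), the squared distance is 0.889, so noncentrality = 20 × 0.889 = 17.8. Critical F (2, 18 df) = 6.01. Power = 78.9%.
- *Mean of both post visits minus baseline.* Variance = 1 + (1 + 0.25)/2 − 2 × 0.25 = 1.125. Noncentrality = √(20/1.125) = 4.22. Power = 89.7%.

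The stated 80% is thus reproduced to within about a point by the T² test. Other readings of the unspecified contrast give other values (62.8% for T² with means 0, 0.5, 1), so the comparison uses the readings that match the plan.

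**Step 2: cut the same data at a threshold.** Let baseline be N(0, 1), follow-up N(−1, 1), correlation 0.25, and abnormal mean above c. The share abnormal at baseline, p, is not in the documents, so it is an assumption: c = Φ⁻¹(1 − p). With Φ₂ the bivariate normal distribution function,

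- P(abnormal → normal) = Φ(c + 1) − Φ₂(c, c + 1; 0.25)
- P(normal → abnormal) = Φ(c) − Φ₂(c, c + 1; 0.25)

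For p = 50%, c = 0: follow-up abnormal 15.9%, discordant probabilities 0.397 and 0.055.

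McNemar power is summed over the number of discordant pairs d ~ Binomial(20, sum of the two probabilities) and their split x. The exact test rejects when the two-sided binomial p-value is at most 0.01; the asymptotic test uses z = (2x − d)/√d. The last column is a simulated paired t-test on baseline 0/1 minus the mean of the two post-visit 0/1 values, with a 1 SD drop at both visits.

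| Abnormal at baseline (assumed) | Abnormal at follow-up | Discordant probabilities | Exact McNemar, one visit | Asymptotic McNemar, one visit | Both visits averaged |
|---|---|---|---|---|---|
| 30% | 6% | 0.269 / 0.033 | 9% | 17% | 21% |
| 50% | 16% | 0.397 / 0.055 | 26% | 35% | 51% |
| 70% | 32% | 0.448 / 0.065 | 32% | 41% | 64% |
| 80% | 44% | 0.423 / 0.060 | 29% | 39% | 64% |

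The one-visit columns compare with 77% on the continuous scale, and the last column with 90%. Outside this range, exact power is 2% at 20% abnormal and 17% at 90%.

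**Step 3: sample size.** For 80% power, exact McNemar needs 61 subjects at 30% abnormal, 44 at 50%, 40 at 70% and 42 at 80%. The 25 subjects named in the Statistics section fall short in every case.

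**The case against.** The strongest reply is that the plan never commits to a yes/no analysis. Resolution is undefined, the logistic link is only an example, means are equally a primary scale, and excess weight loss is also expressed as a percentage. That stands, with one qualification: excess weight loss is a continuous percentage for each patient and does not naturally call for a logistic link, so resolution is the likeliest outcome for the proportion scale. That remains an inference.

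Second, the T² test is tied to weight. No 1 SD shift or 0.25 correlation is given for laboratory values or blood pressure, so no documented power for these outcomes is reduced. That also stands. The 77% to 79% is a like-for-like comparator. It is a fair one because the Statistics section itself extends its claim to all models and to discrete outcomes.

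Third, the size of the loss depends on the test. A Wald test of the difference in proportions, which is liberal at this sample size, gives 40% to 62%, and averaging visits gives 21% to 64%. The plan specifies neither McNemar's test nor a single visit. So no one figure should be quoted, but none of these methods reaches its continuous counterpart.

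Fourth, the Statistics section fixes the effect as 3% of variance explained, and power might be similar on any scale for a fixed share. But cutting a continuous measure lowers the share that the same underlying change explains, so this does not make the choice of scale neutral.

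Finally, AIM 3 is a proof-of-concept study, and a resolution rate has clinical meaning. That supports reporting the rate. It does not support the power claim: AIM 3 also assesses effectiveness and tests at 1%.

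**Conclusion.** The statement that power is unaffected by the scale of measurement is wrong on the plan's own design inputs. Continuous change has 77% (one visit), 79% (T²) or about 90% (both post visits averaged). A yes/no version of the same shift would have 9% to 32% (exact McNemar, one visit), 17% to 41% (asymptotic McNemar, one visit) or about 21% to 64% (both visits averaged). These figures assume two-sided testing, 30% to 80% abnormal at baseline, and a 1 SD shift in measures for which the plan gives none. Separately, resolution and its scale are undefined.

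A reader might go further and infer that the plan puts co-morbidity resolution on a yes/no scale and thereby cuts that outcome's power from 77%. The documents do not support this. They do not define resolution as a cut, do not assign it to proportions, do not drop the analysis of means, and do not give the 77% to 79% to these outcomes.

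**What to change.** - In Statistics, delete the sentence on scale of measurement, and limit the power statement to the continuous contrast in Statistical Power for AIM 3.
- In the Data Analysis Plan, state that each lipid, insulin, glucose and blood pressure measure is analysed primarily as continuous change at 3 and 6 months, on the log scale where skewed.
- Define resolution in advance, including its denominator, and report the proportion resolved descriptively with an exact confidence interval. If only patients abnormal at baseline count, the denominator will be smaller than the full sample for any measure that is not abnormal in everyone.

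The cost is protocol wording. The values are already collected at the required visits. The small downside is that the headline for these measures becomes a mean change, with the resolution rate still reported beside it.

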adolescents with severe obesity have not reported similar sustained weight loss trajectories, particularly in the long-term.¹⁴⁻¹⁹ Yet national adolescent MBS rates have not increased at the same rate of that of the severe obesity epidemic, and short-and long-term attrition (both to and from MBS) remains a significant challenge in this patient population. In fact, there is no standardized pre-and post-operative lifestyle intervention that is offered to adolescent MBS patients to support the behavioral changes that must occur to sustain successful weight loss. Given the extensive evidence-bases for (1) outpatient healthy lifestyle intervention to manage obesity²¹⁻³⁰; and (2) MBS to treat obesity¹¹⁻¹³, there is an opportunity to explore the *combination or partnering* of lifestyle intervention and MBS for adolescents with severe obesity to decrease attrition and improve health outcomes. Our team ([name] et al, 2019)^{31,32} has called attention to the imperative need for research focused on the compound effect of MBS and lifestyle management, and how the timing or sequence of these weight loss approaches influence health outcomes. In other words, the field needs to more rigorously develop, evaluate (feasibility, acceptability) and test for when, and for how long lifestyle interventions (1) should be introduced in adolescents with severe obesity before MBS (for those medically cleared and who are planning on having MBS); and (2) should be included, and at what dosage (as well as specific content and timing) after MBS. Moreover, widening obesity-related health disparities warrant particular attention toward at-risk populations including ethnic minorities, and those with low socioeconomic status who are most impacted by the increase in, and comorbidities associated with severe obesity. Specifically, rigorous qualitative and quantitative research designs (e.g. mixed methods) should be applied to the research questions of (1) how lifestyle interventions can be combined/sequenced with MBS over time to optimize health outcomes; and (2) what critical behavioral strategies of lifestyle interventions from previous documented successes among adolescents with obesity can be enhanced, modified and/or adapted to increase the effectiveness (both in the short and long term) in the MBS patient population so they may enter adulthood with sustainable lifestyle skills to achieve healthier BMI developmental trajectories. As such, we propose the following mixed methods specific aims:

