
Objectives

[figure not shown]
- We will examine how lifestyle interventions combined with bariatric surgery over time can optimize treatment outcomes via the following aims:
- AIM 1.** Generate qualitative data *necessary to adapt* an existing evidence-based healthy lifestyle behavioral intervention's content, strategies and delivery methods to explicitly support pre- and post-MBS, ethnically diverse (non-Hispanic white and black; Hispanic, other), adolescent patients and their families. This formative research will include focus groups, and key informant interviews with adolescents, parents, and clinical team members.
- AIM 2.** *Adapt* the healthy lifestyle behavioral intervention (referenced in AIM 1), as informed by AIM 1 data (and analyses), to support pre-and post-MBS among ethnically diverse adolescent patients and their families.
- AIM 3.** Conduct a *proof of concept study* to assess feasibility, acceptability, and effectiveness of an MBS-supported healthy lifestyle behavioral intervention (*adapted* in AIM 2) among adolescent patients, their families, and their clinical team. Compare social determinants of health (SDOH) screening data with a comparable adolescent patient population from Children's Health.

Hypothesis₁: Acceptability and feasibility (adoption) of an adolescent-targeted multimedia lifestyle intervention sequenced with bariatric surgery with improve 3-and 6-month post-operative health-related outcomes.

Study Design

- This study will employ a mixed-methods design; AIM 1 will focus on qualitative data collection to inform adaptation of the intervention (AIM 2) and AIM 3 will conduct a pilot of the adapted intervention.

Figure 2. Study Schematic Adapted from the Obesity-Related Behavioral Intervention Trials (ORBIT)³³ that focuses exclusively on the early, pre-efficacy phases of behavioral treatment development.

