- A total of 75-85 metabolic and bariatric surgery (MBS) adolescent patients (< 18 years old), their parents and healthcare team will be recruited for the study. This will consist of 40-60 focus group participants (adolescent MBS candidates [n=24-36], their parents [n=16-24], and Key Informant Interviews [N=5]) and 20 for the proof-of-concept trial (AIM 3). Participants will be male and female, Hispanic, non-Hispanic black, non-Hispanic white, and mixed/other ethnicity and will be recruited from one MBS practice at Children's Health System of Texas pediatric weight management clinic. We expect > 45% of the sample to be Hispanic, ≥ 30% to be non-Hispanic black and 5-10% multiethnic and 70% to be female. All study participants who enter the proof-of-concept trial will be followed for 6 months after MBS. There will also be a variety of adult (parent and clinical team) participants who will engage in key informant interviews. These adults will be the parents of the adolescents (n~5-10) and clinical caregivers (n=5). We will collect and analyze the data from the focus groups and key informant interviews. Based on the information gathered, we will develop a *proof of concept study* that would support bariatric patients' pre- surgery and post-surgery. We will then implement the proof of concept study (AIM 3) enrolling approximately 20 ethnically diverse severely obese adolescent participants who have decided to have bariatric surgery/metabolic bariatric surgery (MBS). We will follow these participants for a period of 18

months. This begins when the patients and their parent/caregiver provide consent to participate in the study. After bariatric surgery they will be followed for 6 months with 3-and 6- month measurement assessments. We will evaluate the effectiveness, accessibility, feasibility, and delivery of the program. We will look to identify what participants liked about the program and what they will recommend for improvements moving forward. We will also gather information about the contribution of the intervention in the patient's weight loss outcomes post- surgery. During this process in Aim 3 we will provide a water bottle at their first clinic visit. Upon completion of the surgery participants may receive a FitBit, a scale, workout bands, and weights to aid in their weight loss journey. **Incentives**

- For the focus groups and key informant interviews (AIM 1), participants will be provided with a \$25 gift card.

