- There will be approximately 4 Children's Health sites utilized for the study; COACH Clinic, Children's Medical Center Dallas, Children's Health Plano, and Children's Specialty Center in Dallas. All participants will be recruited at one of these 3 sites. There will be 3 follow-ups with participants in the pilot study. They will be followed over the course of 18 months. This begins 12 months before surgery. During this time the participant will have a preoperative survey and will be given the intervention. After this period they will have two post-operative surveys at 3 months and 6 months respectively. For the focus group and key informant participants they will be required to participate in only one focus group or interview lasting no more than an hour to an hour and a half. If focus group participants are unable to attend focus group due to scheduling conflicts, time constraints or transportation issues they will have the option of participating in an in-depth phone interview, online-video interview or completing a survey. These interviews or survey will also take up to an hour to an hour and a half to complete.
- The PI will also gather medical records of each participants such as pre-surgery BMI and post-surgery BMI and obesity related co-morbidity information to determine the effectiveness of the intervention program in supporting the health outcomes post-surgery. SDOH data will also be pulled from the medical records and will be compared to a similar patient population.

EMR data will be gathered up to 18 months post-surgery.

Study Measures

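### Aim 3's one-group design can show only the combined change after surgery plus the programme, yet four sections present it as programme effectiveness or impact

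*Combined protocol and SAP*

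**What the plan says.** **Design.** Under Study Design, Aim 3 enrols about 20 adolescents who have already chosen MBS. Under Study Measures (Intervention Delivery), all of them are to have at least 6 programme sessions before surgery and 20 after. Statistical Power for AIM 3 describes a single-factor repeated-measures design; the factor is time. Anthropometric and cardiometabolic data are taken at baseline and at 3 and 6 months after surgery, which the Data Analysis Plan counts as one pre-surgery and two post-surgery measurements.

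**Analysis.** Weight change is tested with Hotelling's T². For the Table 2 outcomes generally: "We will use the Generalized Linear Model (GZLM) to model the impact of the intervention developed in AIM 2 for dependent effects". Baseline values enter that model as covariates, justified by balance at pretest and by control of regression to the mean.

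**What the results are said to show.** Objectives, Aim 3, is to "assess feasibility, acceptability, and effectiveness of an MBS-supported healthy lifestyle behavioral intervention". Study Design says that the programme's effectiveness will be evaluated along with its accessibility, feasibility and delivery, and adds: "We will also gather information about the contribution of the intervention in the patient's weight loss outcomes". Study Procedures collects BMI and co-morbidity data before and after surgery "to determine the effectiveness of the intervention program in supporting the health outcomes post-surgery".

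**Framing that points the other way.** The schematic's caption says that the underlying framework "focuses exclusively on the early, pre-efficacy phases of behavioral treatment development". Background Information calls for research on the "compound effect of MBS and lifestyle management". The Statistics section describes the investigation as observational.

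**The concern.** To speak of a programme's effectiveness or impact, one needs some contrast between having the programme and not having it, with surgery held the same. Aim 3 has no such contrast for weight or cardiometabolic outcomes. What it will observe is how patients fare after surgery and programme together.

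At stake is the conclusion. If Study Procedures and the Data Analysis Plan are followed as written, a significant fall in weight or BMI after surgery could be reported as programme effectiveness, although the same result could arise if the programme did nothing. The process aims are not at risk, because a single group suits them.

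**Working it through.** **1. Inputs** (Statistical Power for AIM 3): n = 20, three time points, SD 1, all correlations 0.25, alpha 0.01, contrast value 1, stated power 80%. The contrast coefficients are not given.

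**2. The plan's own figure.** Take the differences 3 months minus baseline and 6 months minus baseline. Each has variance 2(1 − 0.25) = 1.5, and their covariance is 1 − 0.25 − 0.25 + 0.25 = 0.75. With a shift of 1 at both visits, the T² noncentrality is 20 × 2/(1.5 + 0.75) = 17.78, and power on F(2, 18) is 78.9%. For baseline against 6 months alone, the noncentrality is 1/√(1.5/20) = 3.65 on 19 df, and two-sided power is 77.4%. The stated 80% is reproduced closely enough. It is power for the total change over time.

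**3. What the test can see.** Write the surgery effect as s and the programme effect as p. Every patient has both, so the expected change is s + p. In regression terms, the indicators for being after surgery and for being after surgery with the programme are the same column, and only their sum can be estimated. Splitting a total of 1 in four ways (200,000 simulated trials each, baseline against 6 months) gives:

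| s + p | mean estimate | rejected |
|---|---|---|
| 1 + 0 | 1.000 | 77.4% |
| 0.75 + 0.25 | 1.000 | 77.4% |
| 0.5 + 0.5 | 0.999 | 77.3% |
| 0 + 1 | 0.999 | 77.3% |

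The test gives the same answer whether the programme does everything or nothing.

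**4. The pre-surgery sessions do not help.** They could yield a programme-only change if outcomes were measured at their start and again just before surgery. Only one pre-surgery measurement is planned.

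**5. The GZLM.** Its independent variables are not listed. Receipt of the programme is planned for everyone, so no term for assignment can be fitted. Adherence, a process measure, will vary, but patients who attend more may differ in other ways, so an adherence term would be an observational association.

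**6. Baseline covariates.** One group has nothing to balance. In a linear model of change on baseline centred at its mean, the intercept equals the raw mean change, so any regression to the mean in the overall change stays there. The covariates can still serve comparisons between patients.

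**7. Search for a comparator.** Objectives and Study Procedures compare Aim 3 patients with a similar patient population, but on social determinants of health data only. The Oversight text speaks of tabulating events by condition, but no second condition is defined.

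**The case against.** **It is a pilot, and says so.** The study is called a proof of concept, sits in a pre-efficacy phase and is described as observational. The combination of surgery and lifestyle management is a legitimate object, and Aim 3's wording could be read as meaning the combination. No decision rule ties a p-value to a claim about the programme. This stands as mitigation. It does not cover Study Procedures or the Data Analysis Plan, which name the programme or the Aim 2 intervention alone, and it makes the effectiveness wording harder to reconcile with the study's stated phase.

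**The T² sentence attributes nothing.** Correct. A reader might infer that the plan presents the T² result as a test of the programme. The documents do not say so: the impact wording belongs to the GZLM, and the T² sentence speaks only of changes in weight. The point is that neither analysis can separate the two effects.

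**Some wording is ambiguous.** Also correct. Hypothesis 1 reads "Acceptability and feasibility (adoption) of an adolescent-targeted multimedia lifestyle intervention sequenced with bariatric surgery with improve 3-and 6-month post-operative health-related outcomes"; its grammatical subject is acceptability and feasibility, so it is not plainly a claim about programme effect. The contribution sentence in Study Design follows one on participant feedback, "We will look to identify what participants liked about the program and what they will recommend for improvements moving forward", but the text does not say that contribution is participant-reported. The finding does not rest on either.

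**The rejection rates are circular.** Accepted. A reader might take the 77% in the first row of the table as the chance of a false claim for the programme. It is the plan's power curve under the assumption that surgery alone supplies a 1 SD change, and no document states that.

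**Unseen material.** The schematic and the attached grant application are not available here, and the reference list includes an introduction to propensity score methods that the visible text does not call on. None of this supplies a comparator, but the statement that there is none is limited to the visible text.

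**Conclusion.** The point holds, as a mismatch between the design and the stated conclusion. Aim 3 can describe the combined course after MBS plus the programme. It cannot estimate the programme's own effect on weight or cardiometabolic outcomes, whichever of the two planned analyses is used. Four sections (Objectives, Study Design, Study Procedures, Data Analysis Plan) present the outcome data as bearing on programme effectiveness or impact.

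No size can be put on the misattribution, because the documents give no surgery-only effect. All that follows is that a significant pre-post change is compatible with a programme effect of zero.

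A reader might go further and infer that the programme does not work, or that the pilot needs a surgery-only arm to be worthwhile. The documents support neither. They contain no evidence on the programme's effect in either direction, and the feasibility, acceptability, accessibility, delivery and sustainability questions can be answered in one group.

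The conclusion assumes that all Aim 3 patients receive both components as planned, and that no comparator is defined in material not shown.

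**What to change.** Wording only.

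- **Objectives (Aim 3), Study Design and Study Procedures:** replace the programme's effectiveness with *describe changes in health outcomes after MBS plus the programme*. Keep the other evaluation aims and the participant feedback.
- **Data Analysis Plan, GZLM sentence:** state the purpose as *to model change in Table 2 outcomes after MBS plus the intervention developed in AIM 2*.
- **Hypothesis 1 and the contribution sentence in Study Design:** reword so that neither claims a tested programme effect on weight.
- **Add once to the Data Analysis Plan:** *Changes in weight and cardiometabolic outcomes describe the combined course after MBS plus the programme and do not estimate the programme's own effect. Conclusions about the programme itself rest on the process measures (feasibility, acceptability, accessibility, delivery, sustainability), and any adherence-outcome association is exploratory and observational.*
- **Data Analysis Plan, baseline covariates:** drop pretest balance as a rationale, and do not claim that the covariates remove regression to the mean from the overall mean change. They may stay for between-patient effects.

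The cost is giving up a programme-effectiveness claim that the design cannot support. Patients, visits and tests do not change.
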